### **6.7 Clinical Criteria for Early Trial Termination**

Early trial termination will be the result of the criteria specified below:

1. Quality or quantity of data recording is inaccurate or incomplete
2. Poor adherence to protocol and regulatory requirements
3. Incidence or severity of adverse drug reaction in this or other studies indicates a potential health hazard to subjects
4. Plans to modify or discontinue the development of the study drug

In the event of Merck decision to no longer supply study drug, ample notification will be provided so that appropriate adjustments to subject treatment can be made.

### **6.8 Laboratory Procedures/Assessments**

Details regarding specific laboratory procedures/assessments to be performed in this trial are provided below. The total amount of blood/tissue to be drawn/collected over the course of the

trial (from pre-trial to post-trial visits), including approximate blood/tissue volumes drawn/collected by visit and by sample type per subject can be found in the laboratory manual.

Refer to the Trial Flow Chart - Section 6.2 for the schedule of laboratory assessments.

### 6.8.1 Laboratory Safety Evaluations (Hematology, Chemistry, Urinalysis, and Others)

Laboratory tests for hematology, chemistry, urinalysis and others are specified here in Table 8.

**Table 8 Laboratory Tests**

Hematology	Chemistry	Urinalysis	Other
Hematocrit	Albumin	Blood	Serum $\beta$ -human chorionic gonadotropin
Hemoglobin	Alkaline phosphatase (ALP)	Glucose	PT (INR)
Platelet count	Alanine aminotransferase (ALT)	Protein	aPTT
WBC (total and differential)	Aspartate aminotransferase (AST)	Specific gravity	Total triiodothyronine (T3)
Red Blood Cell Count	Lactate dehydrogenase (LDH)	Microscopic exam ( If abnormal results are noted )	Free tyroxine (T4)
Absolute Neutrophil Count	Carbon Dioxide ( $CO_2$ or bicarbonate)	Urine pregnancy test †	Thyroid stimulating hormone (TSH)
Absolute Lymphocyte Count	Uric Acid		Blood for correlative studies
	Calcium		
	Chloride		
	Glucose		
	Phosphorus		
	Potassium		
	Sodium		

Hematology	Chemistry	Urinalysis	Other
	Total Bilirubin		
	Direct Bilirubin ( If total bilirubin is elevated above the upper limit of normal )		
	Total protein		
	Blood Urea Nitrogen		

† Perform on women of childbearing potential only. If urine pregnancy results cannot be confirmed as negative, a serum pregnancy test will be required.

Laboratory tests for screening should be performed within 10 days prior to treatment. Results must be reviewed by the investigator or qualified designee and found to be acceptable prior to dose of trial treatment. Unresolved abnormal laboratory values that are drug-related AEs should be followed until resolution. Laboratory tests do not need to be repeated after the end of treatment if laboratory results are within normal range.

## 7 Reporting and Documentation of Results

### 7.1 Evaluation of Efficacy: Antitumor Effect - Solid Tumors

Subject eligibility will be determined using local assessment (Investigator assessment) based on RECIST 1.1. RECIST 1.1 will also be used by the investigator as the primary measure for assessment of tumor response, date of PD, and as a basis for all protocol guidelines related to disease status (e.g., discontinuation of study treatment).

Only those subjects who have measurable disease present at baseline have received at least 1 treatment with pembrolizumab-based therapy, and have had their disease re-evaluated, will be considered evaluable for response. Subjects who exhibit objective disease progression prior to the end of Cycle 1 will also be considered evaluable.

While either CT or MRI may be utilized, as per RECIST 1.1, CT is the preferred tumor imaging technique in this study. For the abdomen and pelvis, contrast-enhanced MRI may be used when CT with iodinated contrast is contraindicated, or when mandated by local practice. Images (including via other modalities) that are obtained at an unscheduled time point to determine disease progression, as well as imaging obtained for other reasons, but which demonstrate radiologic progression, should also be reviewed by the Investigator. MRI is the strongly preferred modality for imaging the brain. The same imaging technique regarding modality, ideally the same scanner, and the use of contrast should be used in a subject throughout the study to optimize the reproducibility of the assessment of existing and new tumor burden and improve the accuracy of the assessment of response or progression based on imaging.

Although RECIST 1.1 references a maximum of 5 target lesions in total and 2 per organ, this protocol allows a maximum of 10 target lesions in total and 5 per organ, if clinically relevant to enable a broader sampling of tumor burden.

If the Investigator identifies radiographic progression per RECIST 1.1, treatment should continue until PD has been verified.

RECIST guideline version 1.1 is published in the European Journal of Cancer:

E.A. Eisenhauer, P. Therasse, J. Bogaerts, L.H. Schwartz, D. Sargent, R. Ford, J. Dancey, S. Arbuck, S. Gwyther, M. Mooney, L. Rubinstein, L. Shankar, L. Dodd, R. Kaplan, D. Lacombe, J. Verweij. New response evaluation criteria in solid tumors: Revised RECIST guideline (version 1.1). Eur J Cancer. 2009 Jan;45(2):228-47.

### 7.1.1 Initial Tumor Imaging

Initial tumor imaging at Screening must be performed within 28 days prior to the date of allocation. The site study team must review screening images to confirm the subject has measurable disease per RECIST 1.1.

Tumor imaging performed as part of routine clinical management is acceptable for use as screening tumor imaging if it is of diagnostic quality and performed within 28 days prior to the date of allocation and can be assessed by the investigator.

If brain imaging is performed to document the stability of existing metastases, MRI should be used if possible. If MRI is medically contraindicated, CT with contrast is an acceptable alternative.

### 7.1.2 Tumor Imaging During the Study

The schedule of on-trial imaging is outlined in Section 6.1 and Table 6.2. Imaging timing should follow calendar days and should not be adjusted for delays in cycle starts. Imaging should continue to be performed until disease progression, the start of new anticancer treatment, withdrawal from study, death, or end of study, whichever occurs first. All supplemental imaging must be reviewed by the investigator.

### 7.1.3 Response Evaluation Following Surgery

Following CN/MET, little to no residual tumor may be present. Progressive disease is defined as the growth of the primary tumor or appearance of any new tumors following CN/MET as assessed by the Investigator per RECIST 1.1.

Objective response (PR and CR) should be confirmed in subjects with residual disease following CN/MET by a repeat imaging assessment. The imaging for confirmation of response may be performed no earlier than 4 weeks after the first indication of a response is observed. Subjects will then return to the regular imaging schedule, starting with the next scheduled imaging time point. Subjects who receive additional imaging for confirmation do not need to undergo the next scheduled tumor imaging if it is less than 4 weeks later; tumor imaging may resume at the subsequent scheduled imaging time point.

First evidence of PD by RECIST 1.1 should be confirmed by repeat imaging assessment at 4-8 weeks in clinically stable subjects. Clinically stable subjects may continue study treatment until the repeat imaging assessment to confirm PD. In clinically unstable subjects, per the investigator's assessment, neither repeat imaging assessment nor continuation of study treatment may be feasible or in the best interest of the subject.

See section 7.1.6 for further details regarding RECIST 1.1 response criteria.

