### 2.2.2 Secondary

- The clinical efficacy of preoperative pembrolizumab-based therapy in subjects with advanced RCC will be assessed by ORR, defined as CR or PR per Response Evaluation Criteria in Solid Tumors (RECIST) 1.1, modified to allow a maximum of 10 target lesions or 5 target lesions per organ.
- The clinical efficacy of continued pembrolizumab-based therapy in subjects with advanced RCC will be assessed as follows:
  - In subjects who obtain CR or PR/SD with R0 resection and are treated 1 year of pembrolizumab-based therapy:
    - 1-year and 2-year disease-free survival (DFS) rate, and median DFS
  - In subjects who obtain PR/SD and have residual disease following CN/MET and are treated with 1 year of pembrolizumab-based therapy:
    - 1-year and 2-year PFS rate, and median PFS
- Safety will be assessed and reported using National Cancer Institute (NCI) Common Terminology Criteria for Adverse Events (CTCAE) version 5.0
  - Surgical complications will be assessed according to the Clavien-Dindo classification (Appendix 3)

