##### Progressive Disease

At least a 20% increase in the sum of the LD of target lesions, taking as reference the smallest sum of the LD recorded since the treatment started and minimum 5 mm increase over the nadir, or the appearance of 1 or more new lesions.

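### Section 7.1.3's definition of progression after surgery omits growth of residual lesions, which conflicts with the RECIST 1.1 criteria it cites and leaves the PFS event unclear

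*Combined protocol and SAP*

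**What the plan says.** Section 7.1.3 is the only section on response evaluation after surgery. It first notes that little or no tumour may remain, then states: "Progressive disease is defined as the growth of the primary tumor or appearance of any new tumors following CN/MET". The sentence goes on to tie the assessment to RECIST 1.1 ("following CN/MET as assessed by the Investigator per RECIST 1.1"). The section later requires that "First evidence of PD by RECIST 1.1 should be confirmed by repeat imaging assessment at 4-8 weeks in clinically stable subjects", and it closes with "See section 7.1.6 for further details regarding RECIST 1.1 response criteria".

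Section 7.1 sets the general rule: "RECIST 1.1 will also be used by the investigator as the primary measure for assessment of tumor response, date of PD". It makes no exception for the postoperative period.

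Section 7.1.6 gives the criteria. For target lesions, progression is "At least a 20% increase in the sum of the LD of target lesions", measured from the smallest sum since treatment began and with an absolute increase of at least 5 mm, or any new lesion. For non-target lesions it is unequivocal progression of an existing lesion or any new one. Table 9 carries both routes to overall PD, although a footnote limits the non-target route to exceptional circumstances.

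Section 2.2.2 assigns PFS to a group described as "In subjects who obtain PR/SD and have residual disease following CN/MET". Section 8.1 repeats this. Neither defines the PFS event beyond remaining progression-free. Section 8.4.3 reports DFS and PFS descriptively, with Kaplan-Meier medians.

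**The concern.** The sentence in 7.1.3 is worded as a definition and covers exactly the period in which PFS is observed. It allows two routes to progression: growth of the primary, and new tumours. Residual metastases belong to neither.

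For many subjects the first route is closed or nearly so. It closes once the primary has been removed, and inclusion criterion 2 admits subjects whose nephrectomy preceded the study. The PFS group is selected for having disease left behind, so the sentence is silent on the lesions that put a subject in that group. If those lesions grow and no event is recorded, the 1-year and 2-year PFS rates and the median are too high.

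**Working it through.** The documents give no figure to reproduce. The check sets the two rules side by side and applies each to the same subject.

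**What each rule counts after surgery**

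| Finding on a postoperative scan | 7.1.3, literal wording | 7.1.6 and Table 9 |
|---|---|---|
| New lesion | PD | PD |
| Growth of the primary, if still present | PD | PD if the target or non-target threshold is met |
| Residual target metastasis grows, at least 20% and at least 5 mm | Not listed | PD |
| Unequivocal growth of a residual non-target lesion | Not listed | PD (subject to the Table 9 footnote) |

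The rules part mainly in the last two rows, which apply to subjects with macroscopic residual disease (R2). They matter little for the R0 group, whose endpoint is DFS and for whom a new tumour is the natural event.

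**Illustration (lesion sizes are assumed; the documents give none).** Take the postoperative sum of target lesions as the smallest sum. Relative growth = (later − smallest) / smallest.

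- 30 to 37 mm: 7/30 = 23.3%, +7 mm. PD under 7.1.6; not under the literal 7.1.3.
- 20 to 25 mm: 5/20 = 25%, +5 mm. PD under 7.1.6 only.
- 60 to 72 mm: 12/60 = 20%, +12 mm. PD under 7.1.6 only.
- 15 to 18 mm: 3/15 = 20%, but +3 mm. Not PD under either.

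Across this range, every lesion that meets the 7.1.6 threshold is classified differently by the two texts.

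**Reference sum after resection.** Deferring to 7.1.6 does not fully fix the event date. Its reference is the smallest sum since treatment started, and the documents do not say how a resected target lesion enters that sum or whether a postoperative baseline is set. Assume an 80 mm primary and a 30 mm metastasis, unchanged before surgery: 80 + 30 = 110 mm. After nephrectomy the metastasis grows from 30 to 37 mm.

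- Reference 30 mm (postoperative sum): +23.3%, +7 mm, PD.
- Reference 110 mm (preoperative sum): (110 − 37)/110 = 66% decrease, no PD.

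Reading the smallest recorded sum as the postoperative 30 mm is the natural choice, but the plan should say so.

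**The case against.** The strongest reply is that RECIST 1.1 governs throughout. Section 7.1 makes it the measure for the date of PD, the disputed sentence itself ends by invoking it, the confirmation rule speaks of PD by RECIST 1.1, and the section sends the reader to 7.1.6. The PFS endpoint text does not adopt the 7.1.3 sentence. That sentence also follows a remark about little or no residual tumour, so it may have been written with complete resection in mind. Finally, R2 does not specify a site, so residual tumour at the primary site might count as growth of the primary.

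Most of this stands. It shows the probable intent and rules out a stronger reading that a reader might infer: that growth of residual metastases is outside the PFS event altogether. The documents contain a specific statement and a general rule that disagree; they do not contain a settled exclusion. The disagreement remains because 7.1.3 is phrased as a definition for this period and cites 7.1.6 only for further detail.

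Two other inferences are unsupported. A reader might suppose that growth of residual metastases is the main way R2 subjects fail, but the documents give no failure-pattern data. A reader might also try to size the bias from the 15.1-month median PFS in section 1.2.2.1 and an assumed share of uncounted progressions. That median comes from a phase III drug trial, not from subjects with residual disease followed from surgery, and nothing in the documents supports any particular share.

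The objection also limits the consequence. PFS carries no test, alpha or power, and section 8.4.1 calls DFS and PFS exploratory although 2.2.2 and 8.1 list them as secondary.

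**Conclusion.** The point holds as an internal conflict. Section 7.1.3 names only growth of the primary or new tumours, while the criteria it cites also count growth of residual target and non-target lesions. If the literal sentence is followed, such growth in subjects with residual disease after CN/MET is not a PFS event and PFS is overstated. If the RECIST 1.1 references are followed, it is an event, but its date still depends on a reference sum that the plan does not define after resection.

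The direction under the literal reading is clear, but the size cannot be calculated from the documents. The lesion sizes above are assumptions that show only that the rules diverge. The primary endpoint, sample size and power are unaffected. The point deserves correction because PFS events and dates should be reproducible from the text.

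**What to change.** Reconcile 7.1.3 with 7.1 and 7.1.6. For the PFS analysis, state that:

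- an event is RECIST 1.1 progression of any residual target or non-target lesion, or any new lesion;
- resected target lesions are excluded from the reference sum;
- the first postoperative scan (Table 7, week 15) is the starting reference, and the smallest later sum is the nadir.

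The same edit should settle how the Table 9 footnote on non-target lesions applies to the PFS event.

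Keep this wording within the PFS analysis. Progression also governs treatment discontinuation (sections 5.1.4, 6.3.1 and 7.1). There the passages need only be made consistent with each other, and this review does not propose which rule should apply.

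The cost is a few sentences and no new procedure, since the week-15 scan is already scheduled. The postoperative reference is nonetheless an analysis decision as well as a wording repair: growth of a residual lesion between the week-10 and week-15 scans would be absorbed into the new reference. The plan should acknowledge that.

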#### 7.1.4 Disease Parameters

##### Measurable disease

Measurable disease is defined as lesions (or tumors) that can be accurately measured in at least 1 dimension (longest diameter [LD] to be recorded) with a minimum size of 10 mm by CT scan (irrespective of scanner type) and MRI (no less than double the slice thickness and a minimum of 10 mm), and/or 10 mm caliper measurement by clinical exam (when superficial).

All tumor measurements will be recorded in millimeters or decimal fractions of centimeters. Previously irradiated lesions are considered non-measurable except in cases of documented progression of the lesion since the completion of radiation therapy.

##### Target lesions

All measurable lesions up to a maximum of 10 lesions total (and a maximum of 5 lesions per organ) representative of all involved organs should be identified as target lesions and recorded and measured at baseline. Target lesions will be selected on the basis of their size (lesions with the LD) and their suitability for accurate repeated measurements (either by imaging techniques or clinically). A sum of the LD for all target lesions will be calculated and reported as the baseline sum LD. The baseline sum LD will be used as reference by which to characterize the objective tumor response.

##### Non-target lesions

All other lesions (or sites of disease), including any measurable lesions over and above the 10 target lesions, should be identified as non-target lesions and should also be recorded at baseline. It is possible to record multiple non-target lesions involving the same organ as a single item on the case record form (e.g. “multiple enlarged pelvic lymph nodes” or “multiple liver metastases”). Bone lesions may be measurable if  $\geq 1$  cm on MRI. Measurements of these lesions are not required, but the presence or absence of each will be noted throughout follow-up.

##### Non-measurable disease

Non-measurable disease is all other lesions (or sites of disease), including small lesions (LD  $< 20$  mm with conventional techniques or  $< 10$  mm using spiral CT scan). Leptomeningeal disease, ascites, pleural or pericardial effusion, inflammatory breast disease, lymphangitic involvement of skin or lung, abdominal masses/abdominal organomegaly identified by physical exam that is not measurable by reproducible imaging techniques are all non-measurable.

#### 7.1.5 Methods for Evaluation of Measurable Disease

All measurements will be taken and recorded in metric notation using a ruler or calipers. All baseline evaluations will be performed as closely as possible to the beginning of treatment and never more than 28 days before the beginning of the treatment.

The same method of assessment and the same technique will be used to characterize each identified and reported lesion at baseline and during follow-up. Imaging-based evaluation is preferred to evaluation by clinical examination when both methods have been used to assess the antitumor effect of a treatment.

### 7.1.6 Response Criteria

#### Evaluation of Target Lesions

##### Complete Response

Disappearance of all target lesions determined by 2 separate observations conducted not less than 4 weeks apart. Any pathological lymph nodes (whether target or non-target) must have reduction in short axis to <10 mm (the sum may not be "0" if there are target nodes). There can be no appearance of new lesions.

##### Partial Response

At least a 30% decrease in the sum of the LD of target lesions, taking as reference the baseline sum of the LD. There can be no appearance of new lesions.

##### Progressive Disease

At least a 20% increase in the sum of the LD of target lesions, taking as reference the smallest sum of the LD recorded since the treatment started and minimum 5 mm increase over the nadir, or the appearance of 1 or more new lesions.

##### Stable Disease

Neither sufficient shrinkage to qualify for PR nor sufficient increase to qualify for PD, taking as reference the smallest sum of the LD since the treatment started.

#### Evaluation of Non-Target Lesions

##### Complete Response

Disappearance of all non-target lesions and normalization of tumor marker level. All lymph nodes must be non-pathological in size (<10 mm short axis).

##### Incomplete Response/Stable Disease

Persistence of 1 or more non-target lesion(s) and/or maintenance of tumor marker level above the normal limits.

##### Progressive Disease

Appearance of 1 or more new lesions and/or unequivocal progression of existing non-target lesions.

### **Evaluation of Best Overall Response**

The best overall response is the best response recorded from the start of the treatment until PD/recurrence (taking as reference for PD the smallest measurements recorded since the treatment started). The subject's best response assignment will depend on the achievement of both measurement and confirmation criteria (Table 9).

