**Table 9 Response Criteria**

Target Lesions	Non-Target Lesions	New Lesions	Overall Response	Best Response for this Category Also Requires
CR	CR	No	CR	>4 weeks confirmation
CR	Non-CR/ Non-PD	No	PR	
PR	Non-PD	No	PR	>4 weeks confirmation
SD	Non-PD	No	SD	documented at least once >4 weeks from baseline
PD	Any	Yes or No	PD	
Any	PD*	Yes or No	PD	
Any	Any	Yes	PD	no prior SD, PR or CR

Abbreviations: CR = complete response; PD = progressive disease; PR = partial response; SD = stable disease.

\* In exceptional circumstances, unequivocal progression in non-target lesions may be accepted as disease progression

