#### Exploratory endpoints

- The relationship between clinical efficacy (by above measures) and changes in T1ICs (by above measures) will be explored.
- Clinical efficacy: pathologic response rate, R0 resection rate
- The changes in frequency and numbers of circulating T cells will be assessed by flow cytometry.
- Comprehensive assessment will be performed to explore the tumor microenvironment, including for PD-L1 status. Transcriptional profiling of tumor microenvironment

constituents (including T cell subsets, tumor, and stroma) in pre- and post-treatment specimens will be analyzed .

- Changes in the T cell repertoire will be explored via high resolution TCR sequencing, in both blood and tumor specimens.
- Molecular profiling of pre- and post-treatment tumor and normal tissue will be performed to explore biomarkers of response. Neoepitope burden will be assessed.
- Wilcoxon rank-sum test will be used to assess whether there is a relationship between any of the immune cell subsets and objective radiographic response as well as pathologic response. Cox-proportional hazard models will be applied to assess if there is relationship between any of the immune cell subsets and PFS. Parallel analysis will be performed for PD-L1 expression. Wilcoxon rank-sum test will also be used to assess whether the T cell receptor clonality diversity index is different between responders vs. non-responders (defined by objective radiographic response or pathologic response), and between subjects who have progression within 1-year vs. those whose disease has not progressed. Additional analyses of immunocorrelative data are detailed in the procedures manual.

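### The response rule in Section 7.1.6 runs through surgery and needs a confirmation scan that cannot be done before it, so it conflicts with the preoperative ORR endpoint.

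*Combined protocol and SAP*

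**What the plan says.** Section 2.2.2 sets the scope of the endpoint: "The clinical efficacy of preoperative pembrolizumab-based therapy in subjects with advanced RCC will be assessed by ORR". Section 8.1 repeats this, and Section 8.4.3 has ORR reported descriptively following preoperative therapy. Section 3.1 places a RECIST assessment after 9 weeks, and Section 6.1.2.4 requires the week-10 scan before CN/MET.

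The assignment rule is in Sections 7.1.4 and 7.1.6:

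- Window: "The best overall response is the best response recorded from the start of the treatment until PD/recurrence".
- Reference: "The baseline sum LD will be used as reference by which to characterize the objective tumor response".
- PR: "At least a 30% decrease in the sum of the LD of target lesions, taking as reference the baseline sum of the LD".
- CR: disappearance of all target lesions, "determined by 2 separate observations conducted not less than 4 weeks apart".
- Best response depends on both measurement and confirmation. For CR and PR, Table 9 asks for ">4 weeks confirmation".

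Section 7.1.3, on response after surgery, adds: "Objective response (PR and CR) should be confirmed in subjects with residual disease following CN/MET by a repeat imaging assessment". It names no reference sum. The Abstract also speaks of subjects reaching CR either before or after CN/MET. No section removes resected lesions from the sum, sets a postoperative baseline, or ends response assignment at surgery.

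**The concern.** Target lesions are chosen partly by size, so an intact primary will often be among them, and CN/MET removes it. If the sum of diameters is then compared with the pre-treatment baseline, the fall reflects the operation. An endpoint intended to describe 9 weeks of drug therapy could take in that mechanical effect.

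The same label feeds the mechanistic analyses. Section 8.1 plans: "Wilcoxon rank-sum test will be used to assess whether there is a relationship between any of the immune cell subsets and objective radiographic response". It also compares T-cell receptor clonality between responders and non-responders. Neither comparison says that response means preoperative response. Subjects with SD counted as responders would blur the contrasts the correlative work is designed to detect.

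**Working it through.** The plan gives no target rate, sample size or power for ORR, so there is no figure to reproduce. The check covers the schedule, then the scoring rule.

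**Schedule** (day 1 = Cycle 1 Day 1, cycles on time)

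- Week-10 scan (Section 6.1.2.4, ±3 days): 9 × 7 + 1 = day 64, so day 61-67.
- End of preoperative treatment: 3 × 21 = day 63.
- Surgery 14-21 days later (Sections 5.1.2.2 and 6.1.2.5): 63 + 14 = 77 to 63 + 21 = 84.
- Scan to surgery: shortest 77 − 67 = 10 days, longest 84 − 61 = 23 days.
- Earliest confirmation, 28 days after the scan: 61 + 28 = 89 to 67 + 28 = 95.
- Next scheduled scan, week 15 (Table 7): 14 × 7 + 1 = day 99 ± 3, so day 96-102.

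The latest on-schedule surgery (day 84) precedes the earliest confirmation (day 89). The visit window does not change this. If Cycle 3 Day 1 (day 43) moves by 3 days, Cycle 3 Day 21 falls on day 60-66 and surgery on day 74-87, still before day 89. Week 10 is the only scheduled on-treatment scan before surgery, so a scheduled scan cannot confirm a preoperative response before an on-schedule operation.

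That leaves three readings of the same text:

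1. Confirmation may be postoperative. It is then read after target lesions have been removed.
2. Confirmation must be preoperative. Then no subject operated on schedule has a confirmed response on scheduled scans.
3. Confirmation is waived for ORR. No section says so.

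**Scoring** (lesion sizes assumed, for illustration only)

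- Baseline: primary 80 mm, lung 18 mm and 12 mm; sum 110 mm.
- Week 10: 78 + 20 + 14 = 112 mm; (112 − 110)/110 = +1.8%, SD.
- After nephrectomy, lung lesions unchanged since week 10: 20 + 14 = 34 mm; (110 − 34)/110 = 69.1% fall, which meets PR. A repeat scan at least 4 weeks later would confirm it.
- Over the same period the lung lesions grew from 30 to 34 mm: 4/30 = +13.3%.

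In general, if resected lesions make up at least 30% of the baseline sum and the remaining lesions have not grown enough to offset this, the PR threshold is met with no drug effect. If all target lesions are resected, the target response is CR.

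**How far the readings could diverge.** Let s be the share of preoperative SD subjects scored as responders because of resection. With 10% preoperative progression (Section 3.1), literal ORR = ORR_pre + s × (1 − 0.10 − ORR_pre). The protocol's background rates (Section 1.1) serve as stand-ins for ORR_pre:

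| ORR_pre | s = 0 | s = 0.5 | s = 1 |
|---|---|---|---|
| 34% (monotherapy) | 34% | 34 + 0.5 × 56 = 62% | 90% |
| 59.3% (combination) | 59.3% | 59.3 + 0.5 × 30.7 = 74.65% | 90% |

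The documents do not give s, and the stand-in rates are not 9-week preoperative rates. The table shows sensitivity to the wording; it is not a forecast.

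**The case against.** The strongest reply is that the endpoint is already confined to the preoperative phase. Sections 2.2.2, 8.1 and 8.4.3 all say so, the week-10 scan is mandatory before surgery, and best overall response is not named as an endpoint in Section 8. On this view Section 7.1.6 is generic RECIST text that yields to the study-specific wording, and the correlates refer back to the efficacy measures listed above them. Much of this stands: a careful analyst could report a clean ORR from the week-10 scan, and no section says that removing a lesion counts as a response. But the label does not settle the matter. Section 7.1.6 makes the assignment depend on confirmation, and the schedule puts confirmation after surgery. To get the clean ORR, the analyst must set aside a written rule.

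Three stronger inferences are tempting, and the documents do not support them:

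- That nearly every operated subject becomes a responder. This is s = 1, an upper bound resting on assumed sizes. Section 3.3.1 admits subjects who have already had a nephrectomy, and subjects with preoperative PD leave the study after surgery or biopsy.
- That the assessment of continued therapy is equally compromised. It rests on DFS and PFS. Progression in Section 7.1.6 is judged from the smallest sum recorded (34 mm in the example, not 110 mm), and Section 7.1.3 has its own postoperative definition of PD.
- That the trial's decisions are at risk. Sample size and interim rules use the immune-cell endpoint. ORR has no hypothesis, threshold or stopping rule.

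**Conclusion.** The rule is wrong as written, with moderate severity because ORR is secondary and descriptive. Followed literally, it either confirms response on scans taken after target lesions were removed, or leaves every subject operated on schedule without a confirmed response. It can also turn preoperative SD into PR or CR. Two analysts working from the same data and protocol could report different ORRs and different responder groups for the exploratory comparisons. It would go too far to say that the reported ORR will be inflated; that depends on which text the analyst follows.

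The timing result assumes that treatment and surgery run on schedule and that response is first seen on the week-10 scan. Subjects who do not have surgery are not affected. The number of subjects misclassified cannot be derived from the documents.

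**What to change.** - Sections 7.1.6, 8.1 and 8.4.3: state that ORR is the response on the week-10 preoperative scan against the pre-treatment baseline, that the confirmation requirement of more than 4 weeks does not apply to it, that it is reported as unconfirmed, and that this assignment closes at CN/MET.
- Section 7.1.3: exclude resected lesions, and use the first postoperative scan (week 15, already scheduled) as the new reference sum for any response reported in subjects with residual measurable disease.
- Section 8.1, exploratory endpoints: state that the responder comparisons use the preoperative response.

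The cost is protocol wording and one CRF field for the postoperative reference sum; no scan is added. The downside is that the ORR is unconfirmed, so it is not directly comparable with confirmed rates such as the 34% cited in Section 1.1, and it may be lower than under the literal rule.
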